6. STUDY PROCEDURES

6.1. Study Measurements and Assessments

6.1.1. Assessment of Primary Endpoint

The difference in the overall and heart failure related healthcare costs between subjects treated with the Furoscix Infusor through 30 days post discharge from the emergency department compared to propensity score matched controls treated in the hospital for \leq 72 hours through 30 days post discharge. Overall and heart failure related healthcare costs comprised of all direct medical costs attributable to healthcare resource utilization incurred overall and for treatment of HF.

6.1.2. Assessment of Secondary Endpoints

The difference in the measurements listed below between subjects treated with the Furoscix Infusor 30 days post discharge from the emergency department compared to propensity score matched controls treated in the hospital for \leq 72 hours through 30 days post discharge.

1. Number of hospital admissions and duration with-in 30 days post discharge from the emergency department
2. Number of HF-related hospital admissions and duration with-in 30 days post discharge from the emergency department
3. Number of HF-related emergency department visits with-in 30 days post discharge from the emergency department
4. Number of HF-related clinic visits with-in 30 days post discharge from the emergency department
5. Description of health-related quality of life using the KCCQ-12 (for the Furoscix Infusor arm only)
6. Change in BNP or NT-proBNP (for Furoscix Infusor cohort only)
7. Subject and/or caregiver satisfaction with Furoscix Infusor (for Furoscix Infusor cohort only)

6.1.3. Safety Assessments

The Furoscix treatment cohort will be monitored for adverse events, and any adverse events will be recorded and reported according to guidelines specified by the United States Food and Drug Administration. Reactions at the infusion site and frequency of these reactions will be recorded as part of the safety assessments.

6.2. Study Phases and Procedures

The Screening Phase will be conducted in the emergency department in a collaborative effort between the emergency physician and the cardiologist. All Subjects who sign the informed consent form and satisfy the inclusion/exclusion criteria will be enrolled into the trial on the same day as screening. Study drug administration can start on the day of screening and enrollment, and administration may commence either in the emergency department or at home.

Furoscix will be administered daily via the Furoscix Infusor whereby 80 mg is administered subcutaneously over 5 hours in a biphasic regimen (30 mg in the first hour, followed 12.5 mg/hour for the subsequent 4 hours). Within a single 24-hour period, the 80 mg dose can be repeated at the discretion of the investigator \geq 2 hours after the completion of the first dose. Subjects should be transitioned back to their oral maintenance diuretic regimen when clinically indicated at the discretion of the investigator (approximately 4 doses). After Subjects have been transitioned to their oral maintenance diuretic regimen, additional doses of Furoscix can be prescribed during the 30-day study period as needed based on the presence of clinical triggers (dyspnea on exertion, edema, and/or excess weight gain) as determined by the investigator. No more than 7 doses of Furoscix is permitted during the

[figure not shown]
30-day study period. Additional doses beyond 7 requires approval by the medical monitor. If subjects receiving Furoscix are hospitalized for heart failure during the treatment period, Furoscix should be discontinued and the subject treated with IV diuretics as clinically indicated. In addition to the scheduled phone and clinic visits, the investigator can utilize unscheduled clinic or phone visits for additional assessments at any time.

Prior to leaving the emergency department on Day 0, the subject and/or caregiver will be trained by the study staff on how to prepare the study product and apply it to their abdomen and remove it once the infusion is completed. The initial dose of the study product may be administered on the day of enrollment. Some subjects may not require their initial dose until the next day. Doses will be provided to the patient for self-administration or administration by a caregiver in the home setting as directed by the investigator or study staff. No more than 7 doses of Furoscix are permitted during the 30-day study period unless approved by the medical monitor. Planned in-person follow-ups include a clinic visit occurring between Days 2-4 and a clinic visit on Day 30±3 days. Scheduled remote follow-ups conducted by telephone by a HF nurse, or designee, will occur on Days 1 and 7, and one call between Days 14-21. Unscheduled at-home telephone calls and unscheduled in-clinic visits may be performed if felt clinically indicated by the study team or the clinical provider.

The Follow-Up Phase will occur on Day 30±3 days for a post treatment follow-up visit completing Subjects' study participation.

Refer to [Figure 2](#) for an overview of study phases and procedures. Note that the depiction in [Figure 2](#) of Furoscix administrations after Day 1 is for demonstration purposes. Again, the investigator can prescribe additional Furoscix dosing and administration at his/her discretion as long as this does not conflict with safe use practices as defined in this protocol and supplementary materials.

Figure 2: Study Phases and Procedures

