STUDY ASSESSMENTS AND PROCEDURES	Patients will be assessed in the emergency department by the investigator and/or study staff for signs and symptoms of worsening HF due to congestion or fluid overload. If it is determined by the investigator that the patient requires parenteral diuresis or continued diuresis outside of the ED care setting, and meets all study eligibility criteria, he/she may be consented and enrolled into the study.

	
The treatment comprises a 5-hour subcutaneous infusion of Furoscix via the Furoscix Infusor. Subjects will be instructed on the use of the Furoscix Infusor by the investigator and/or study staff in accordance with the instructions for use. The initial dose of the study product may be administered on the day of enrollment. Some subjects may not require their initial dose until the next day. Doses will be provided to the subject for self-administration or administration by a caregiver in the home setting as directed by the investigator or study staff. No more than 7 doses of Furoscix are permitted during the 30-day study period. If a subject uses the allotted 7 doses and additional doses are required to control signs and symptoms of congestion when oral diuretics are not effective, approval by the medical monitor is required. Subjects will receive scheduled at-home telephone calls from a HF nurse, or designee, on Days 1 and 7, and one call between Days 14-21. Unscheduled calls can be conducted as needed. Planned in-clinic visits will be conducted between Day 2-4 and then Day 30±3 days. Unscheduled at-home telephone calls by an HF nurse, or designee, and unscheduled in-clinic visits may be performed if felt clinically indicated by the study team or the clinical provider.
 
The study period will be up to 30 days after enrollment. All outcomes will be assessed up to 30 days after the initial discharge from the emergency department.

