6.2.6. Day 30 ± 3 days (In-Clinic Visit)

The following procedures/assessments will be performed at the Day 30 in-clinic visit:

- Directed medical history and medication review
- Cardiopulmonary Exam focused on signs and symptoms of congestion
- NYHA Classification
- Weight for BMI
- Vital Signs

- Venous blood for clinical chemistries, hematology, BNP or NT-proBNP
- Administer the KCCQ-12
- Abdominal skin assessment
- Assessment of adverse events
- Assessment of interval hospitalization, emergency department visits, or unscheduled clinic visits
 - Been admitted to the hospital
 - Been admitted to the hospital for HF-related issues
 - Been seen at the emergency department for HF-related issues
 - Been seen in an outpatient clinic (including immediate care clinic) for HF-related issues
 - Sought any additional or new medical treatment for HF-related issues

Information regarding HF-related healthcare utilization collected before and at the 30-day in-clinic visit will be verified by the investigator through subjects' medical records.

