7. ADVERSE EVENTS

The Investigator is responsible for the detection and documentation of events meeting the definition of an adverse event (AE) or serious adverse event (SAE) as provided in this protocol. AEs will be assessed continuously through the last study visit unless the nature of the AE or SAE requires continued monitoring. All AEs are recorded as mild, moderate or severe, and as Not Related, Possibly Related, Probably Related, and Definitely Related to the investigational product.

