3.5.3. Step 2: Produce Candidate Pool for Historical Cohort

EPI-Q will produce a candidate pool from which historical controls will be drawn via propensity match for comparison against the Furoscix Infusor cohort. This candidate pool will be comprised of HF-patient lives contained in the Marketscan Commercial Claims and Encounters (CCAE) and Medicare Supplemental Database. This pool will contain HF patients who will be characterized by binary indicators consistent with the demographic and background clinical variables (except laboratory tests) that are collected for the Furoscix Infusor arm (Appendix B).

Initially, the historical cohort will be created using the Marketscan Commercial Claims and Encounters (CCAE) and Medicare Supplemental Database for the years 2015-2017. The historical cohort will be later updated post acquisition of latest data up to year 2019.

The following inclusion criteria will be applied to identify patients with worsening HF:

1. Inpatient claims coded with an HF (ICD-9/ICD-10) diagnosis codes in primary position on the claim
2. Worsening HF defined by all admissions coded with a diagnosis-related group (DRG) for HF (291, 292, or 293)
3. Length of Stay 1-3 days
4. Service Category included ED Visit
5. Age 18-80 years
6. Continuous enrollment for 1 year before and 3 months after the index date
7. Background therapy including oral furosemide equivalents daily (Torsemide or Bumetanide)

First qualifying claim, where all the eligibility criteria is met, will be defined as the index date. Patients will be excluded if one of the following exclusion criteria is met:

1. Presence of diagnosis code for a complicating condition, other than HF (e.g. MI, pneumonia) as identified from the prospective arm data before final matching
2. Presence of diagnosis or procedure code for acute renal failure or Dialysis
3. Estimated Creatinine Clearance (CrCl) <30 (indicated by presence of diagnosis code for chronic kidney disease stage 4/5, ESRD or renal failure).

For the patients that meet all the eligibility criteria, the following demographic and baseline characteristics (i.e., candidate variables for propensity score calculation) will be determined and reconciled between the prospective study and historical controls' databases (i.e., only variables that can be consistently defined will be analyzed):

- Integer age
- Sex
- Geographic region (Northeast, North Central, South, West, Unknown)

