3.5.3.1. Healthcare Resource Utilization (HCRU) and Costs

For each patient in the historical control and prospective arm, 30-day follow-up HF-related and all-cause healthcare resource utilization (HCRU) will be estimated and reported.

For cost inputs, events that are major contributors of the costs will be included in the analysis, including any visits and hospitalizations that are either HF-related or all-cause. Using the dataset created for matching, cost benchmarks for each event (HF-related and all-cause) i.e. mean and standard deviation will be derived. For each patient in the historical and prospective cohorts, 30-day HF-related and overall costs will be estimated by summation of applied cost benchmarks to each resource utilization event observed during the 30-day period starting from the beginning of HF-worsening episode.

Overall cost of care will include cost attribute to all-cause HCRU. Total HF-related medical costs will be comprised of the hospitalization costs and outpatient visits costs attributable to HF-related HCRU (defined by claims with a primary diagnosis of HF). All costs will be inflated to \$2019 using Medical Care Consumer Price Index (CPI). All costs included will be gross costs including payer and patient costs.

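### A final visit on Days 27–29 ends participation before the 30-day outcome window closes, so cost and event counts can be slightly understated in the Furoscix arm only

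*Protocol*

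**What the plan says.** **When follow-up ends.** Protocol 6.2: "The Follow-Up Phase will occur on Day 30±3 days for a post treatment follow-up visit completing Subjects' study participation".

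**Outcome window.** The Protocol Synopsis (Study Assessments and Procedures) says: "All outcomes will be assessed up to 30 days after the initial discharge from the emergency department". SAP 3.5.3.1 starts the clock elsewhere. It sums cost benchmarks, in both cohorts, over each "resource utilization event observed during the 30-day period starting from the beginning of HF-worsening episode".

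**Capture in the Furoscix arm.** Subjects are asked about admissions, ED visits and clinic visits at each visit and call, and the last planned contact is the final visit. Protocol 6.2.6 adds a record step: "Information regarding HF-related healthcare utilization collected before and at the 30-day in-clinic visit will be verified by the investigator". On adverse events, Protocol 7 says: "AEs will be assessed continuously through the last study visit unless the nature of the AE or SAE requires continued monitoring".

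**Capture in the control arm.** SAP 3.5.3 requires: "Continuous enrollment for 1 year before and 3 months after the index date".

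**Analysis.** The primary analysis uses the evaluable population, meaning treated subjects who completed all study phases per protocol (SAP 3.3.1.3 and 3.3.4). Missing data in the prospective arm are not imputed (SAP 3.3.2). The SAP has no adjustment for observed person-time.

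**The concern.** Cost and secondary endpoints 1–4 are totals over 30 days. A subject whose final visit falls on Day 27 is compliant and evaluable and is not flagged as having missing data. Days after that visit contribute zero events and zero cost, although nobody has checked them. A late visit does not offset an early one, because events on Days 31–33 lie outside the window.

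Controls have no such gap. Unobserved days can only lower the Furoscix totals or leave them unchanged, which is the direction of the trial's hypothesis. Propensity matching cannot remove the difference, because it comes from how outcomes are ascertained and not from baseline imbalance. A larger sample does not shrink it. Both cost measures and secondary endpoints 1–4 are exposed.

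**Working it through.** **1. The plan's own figure.** Inputs from Protocol 8.1 and SAP 3.3.3: difference 8,600 − 6,500 = $2,100, SD $3,045, 80% power, two-sided 5%.

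n per group = 2 × [3,045 × (1.960 + 0.842) / 2,100]² = 33.005, rounded up to 34. Exact t-test power at 34 per group is 80.0%. The stated 34 is reproduced.

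On the same inputs, the standard error of the difference is 3,045 × √(2/34) = $739. This treats the groups as independent with 1:1 matching.

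**2. Days lost.** Lost days = max(0, last day of window − visit day), with the visit day counted as observed. The documents do not give the distribution of visit days, so an even spread over Days 27–33 is assumed for the mean.

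| Window | Day 27 | Day 28 | Day 29 | Days 30–33 | Maximum | Mean |
|---|---|---|---|---|---|---|
| Protocol, ends Day 30 | 3 | 2 | 1 | 0 | 3/30 = 10% | 6/7 = 0.86 day (2.9%) |
| SAP, counted as Days 0–29 | 2 | 1 | 0 | 0 | 2/30 = 6.7% | 3/7 = 0.43 day (1.4%) |

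**3. Cost effect.** The documents give no readmission risk. Assume 20%–25% over 30 days, $8,600 per event, spread evenly over the window.

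Daily cost = 0.20 × 8,600 / 30 = $57.3, up to 0.25 × 8,600 / 30 = $71.7.

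| | Protocol window | SAP window (Days 0–29) |
|---|---|---|
| Day 27 visit | × 3 = $172–$215 | × 2 = $115–$143 |
| Average, even spread | × 0.857 = $49–$61 | × 0.429 = $25–$31 |

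The average runs from 25/2,100 = 1.2% to 61/2,100 = 2.9% of the design difference. A Day 27 visit runs from 115/2,100 = 5.5% to 215/2,100 = 10.2%.

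**4. Sensitivity to how cost is spread.** Take instead the $6,500 planning mean and assume a share of it accrues evenly over follow-up (protocol window):

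| Share spread evenly | Every visit on Day 27 | Visits spread evenly |
|---|---|---|
| 25% | $162 | $46 |
| 50% | $325 | $93 |
| 100% (ceiling) | $650 | $186 |

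The 100% row is only a ceiling, because the index ED cost falls at the start of the window.

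**5. Effect on the test.** An average bias of $49–$61 is 0.07–0.08 standard errors. With no true difference, a single two-sided 5% test would reject about 5.1% of the time at a bias of $61, and 6.0% at $215 (every subject seen on Day 27).

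**The case against.** **The 30-day requirement is already there.** The Synopsis says outcomes are assessed to 30 days, Protocol 5.7 records concomitant therapy through Day 30, and Protocol 6.2.7 allows unscheduled calls or visits at any time. This stands in part: the intention is stated. What is missing is a procedure that carries it out after an early final visit. Unscheduled contacts are discretionary. The record step verifies only HF-related information "collected before and at the 30-day in-clinic visit", so it neither extends collection nor covers all-cause use. An admission is a serious adverse event (Protocol 7.5), but the exception for monitoring beyond the last visit depends on the nature of an event and does not provide for finding new ones.

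**Three days may be too many.** This stands. Counted as Days 0–29, the SAP's costing window gives a maximum of 2 days. Both readings are possible, so both are shown.

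**The effect is too small to matter to the primary test.** This largely stands for the average. A reader might infer serious false-positive inflation, since an extreme case reaches 21.4%. That case needs every subject seen on Day 27 and all of an $8,600 mean cost spread evenly over follow-up, and nothing in the documents supports it.

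**Dosing after the final visit.** A reader might also infer that doses could be given after an early final visit with no study contact. The documents do not establish this. Protocol 6.2 calls the visit post-treatment and says it completes participation, and Protocol 5.11 limits the product to enrolled subjects. At most, that description and the wording in the same section on additional doses during the 30-day study period must be reconciled.

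**Conclusion.** The gap is real, affects only the Furoscix arm and can only favor that arm. These conclusions follow from the text and need no assumption. Its maximum is 3 days (10%) or 2 days (6.7%) per subject, depending on which 30-day window applies.

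The dollar size is conditional. With a 20%–25% readmission risk at $8,600 and visits spread evenly, it averages about $25–$61, or 1%–3% of $2,100, against a standard error of about $739. For a Day 27 visit it is $115–$215. It would be larger if visits cluster early, and zero for visits on Day 30 or later. The documents support a possible small understatement; they do not show that one will occur or that it would decide the primary result. The change is still worth making, because the bias is systematic and cheap to remove.

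**What to change.** 1. Close the gap by either route; one is enough.
   - Set the final visit no earlier than the end of the outcome window, for example Day 30 to Day 33.
   - Or keep the present window and, for any subject seen earlier, require a brief check of all-cause and HF-related utilization and adverse events, with record review, on or after Day 30.
2. In the SAP, define one start day and one end day for the 30-day window, identical in both arms, and reconcile the Synopsis (from ED discharge) with SAP 3.5.3.1 (from the start of the worsening episode). Specify both ends: adding only an end at Day 30 gives 31 days if Day 0 counts.
3. Reconcile the two statements in Protocol 6.2 on dosing during the study period and the post-treatment final visit.

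With item 1 in place, lost days fall to 0, and the planned 34 per group is unchanged. The cost is some wording, plus slightly less scheduling flexibility under the first route or one short call and record review per early attender under the second.

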6.2.1. Screening Phase (Day 0)

The initial Screening assessment will be conducted the same day as the start of the Treatment Phase and will occur in the emergency department.

The following procedures/assessments will be performed at Screening:

- Informed consent (must be completed prior to any of the following procedures)
- Eligibility review
- Medical history and Subject demographics
- Cardiopulmonary Exam including NYHA Classification
- Weight and height obtained for body mass index (BMI)
- Vital Signs
- Venous blood for clinical chemistries, hematology, BNP or NT-proBNP
- Urine pregnancy test on females of child bearing potential
- Administer the KCCQ-12 (short form)
- Perform site skin assessment where the study product will be placed
- Record concomitant medications (all medications taken within 7 days prior to dosing)
- Study product training with subject and/or caregiver
- Assessments and laboratory tests done as usual care within 12 hours of study enrollment may be collected and entered into the eCRF for the study.

6.2.2. Treatment Phase (Day 0 – Discretion of the investigator)

After the screening activities have been completed and eligibility confirmed, the subject may be enrolled into the Treatment Phase.

The treatment includes a daily, preprogrammed bi-phasic 5 hour drug administration via the Furoscix Infusor. Eighty (80) mg is administered subcutaneously over 5 hours in a biphasic regimen (30 mg in the first hour, followed 12.5 mg/hour for the subsequent 4 hours). Within a single 24-hour period, the 80 mg dose can be repeated at the

discretion of the investigator \geq 2 hours after the completion of the first dose. Subjects should be transitioned back to their oral maintenance diuretic regimen when clinically indicated at the discretion of the investigator (approximately 4 doses). After Subjects have been transitioned to their oral maintenance diuretic regimen, additional doses of Furoscix can be prescribed during the 30-day study period as needed based on the presence of clinical triggers (dyspnea on exertion, edema, and/or excess weight gain) as determined by the investigator. No more than 7 doses of Furoscix is permitted during the 30-day study period. Additional doses beyond 7 requires approval by the medical monitor.

Prior to leaving the emergency department on Day 0, the subject and/or caregiver will be trained by the study staff on how to prepare the study product and apply it to their abdomen and remove it once the infusion is completed. The initial dose of the study product may be administered on the day of enrollment. Some subjects may not require their initial dose until the next day. Doses will be provided to the patient for self-administration or administration by a caregiver in the home setting as directed by the investigator or study staff.

For all treatment days, these data will be recorded in the Subject Diary daily by the subject and reported to the study staff during phone contacts:

- Infusor start and stop times for each dose
- Diuretic use in addition to the study drug (name, route, dose)
- Assessment for adverse events
- Assessment for interval hospitalizations, emergency department visits, or unscheduled clinic visits

The subject will be reminded to complete the Subject Diary daily for each dose, recording the start and end time for each dose and any issues preparing the dose.

